
STATISTICAL METHODS:
 
The trial will be unblinded and primary analysis will be conducted after the 24 week Double-blind treatment period.
 
The primary efficacy variable, (A-a)DO₂, will be tested using an analysis of covariance (ANCOVA) model. This model will have change from baseline to Week 24 in (A-a)DO₂ as the response variable, whilst treatment group and baseline (A-a)DO₂ will be predictor variables. The mean difference between each active dose and placebo in change from baseline of (A-a)DO₂ will be estimated, along with its 95% confidence interval (CI) and associated statistical significance test.
 
The key secondary endpoints of change from baseline in 6MWD and in SGRQ will be analysed using the same ANCOVA model as for (A-a)DO₂. Time to WLL will be analysed by logrank test.
 
Comparisons (for the primary and key secondary endpoints) will be carried out as follows. The first will be of once daily dosing vs. placebo, and the second will be of intermittent dosing vs. placebo. These comparisons will be made in sequence: the once daily dosing group will first be compared with placebo for the primary endpoint and, if significant at P$<$0.05, then the 3 key secondary endpoints will be tested at an overall 5% significance level using the Hochberg procedure. If the test is significant for all of the key secondary endpoints, then the hierarchical testing will proceed with comparing intermittent dosing vs. placebo for the primary, and then the key secondary, endpoints in the same manner as for once daily dosing vs. Placebo.
 
Subjects who withdraw early will have (A-a)DO₂ measurement values imputed by multiple imputation used as their endpoint. Sensitivity analyses will be described in the Statistical Analysis Plan (SAP).
 
Analyses pertaining to the Further Secondary Endpoints will be described in the SAP.
 
Data from the Follow-up period will be reported descriptively in a separate Follow-up report.
	

TRIAL PERIOD:
 
The duration of trial participation for each subject is approximately 50 to 78 weeks:
 
 • Screening period for the subjects is 14 days (+/- 7 days) • Double-blind period up to 24 weeks (+/- 7 days) • Open-label period for 24 or 48 weeks (+/- 14 days) 	

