12 STATISTICAL METHODS AND DETERMINATION OF SAMPLE SIZE

12.1 Statistical and Analytical Plans

The trial will be unblinded and the primary analysis will be conducted after all subjects have completed the 24-week Double-blind period.

A separate SAP, which will provide the technical details of the statistical analysis outlined below, will be prepared for use in conjunction with this protocol.

Before the trial is unblinded, a blind review of the data will be completed. At that time, adjustments to the planned analyses may be identified based on, for example, the extent and timing of missing data. Confirmation of eligibility for analysis populations (see *Section 12.1.1*) will be confirmed at this time.

The data from the open-label Follow-up period will be presented descriptively.

The following details are related to the randomised, double-blind portion of the trial.

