12.1.3 Statistical Issues

Level of Significance, Multiple Comparisons and Multiplicity

For all significance tests, exact p-values (to four decimal places) will be calculated and quoted.

There is one primary efficacy parameter although there are three key secondary efficacy endpoints which are intended to support conclusions based on the primary parameter. In addition, several other endpoints will be considered as descriptive and supportive, and no adjustments for multiplicity will be made for these analyses.

Two comparisons (for the primary and key secondary endpoints) will be carried out. The first will be of once daily dosing vs. placebo and the second will be of intermittent dosing vs. placebo. These two comparisons are not independent of each other and to account for multiplicity, a hierarchical procedure will be used (see below).

See also *Section 12.1.5 Primary Efficacy Analysis*.

Type I Error for Primary and Key Secondary Endpoints

The primary endpoint of (A-a)DO₂ will first be tested for the once daily dosing group versus placebo and, if significant at P<0.05, then the 3 key secondary endpoints will be tested at an overall 5 % significance level using the Hochberg procedure. If the test is significant for all of the key secondary endpoints, then the hierarchical testing will proceed with comparing intermittent dosing vs. placebo for the primary, and then the key secondary, endpoints in the same manner as for once daily dosing vs. placebo.

Full details will be provided in the SAP.

Handling of Dropouts and Missing Data

Different approaches will be used for handling missing data for different endpoints; each is described below for the primary and key secondary endpoints. The efficacy variables will also be analysed using Observed Cases for the PPS.

Adjustment for Covariates

In all analyses of 'change from baseline', the baseline value of the parameter being analysed will be included in an analysis of covariance (ANCOVA) model. The stratification factor 'WLL within 2 months prior to the baseline visit' will be included in all analysis models.

Multicentre Trial

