12.1.5 Primary Efficacy Analysis

The primary efficacy variable, (A-a)DO₂, will be tested using an ANCOVA model. This model will have change from baseline to Week 24 in (A-a)DO₂ as the response variable, whilst treatment group, WLL within 2 months prior to randomisation, and baseline (A-a)DO₂ will be predictor variables. The mean difference between each active dose and placebo in change from baseline of (A-a)DO₂ will be estimated, along with its 95% confidence interval (CI) and associated statistical significance test.

Subjects who withdraw from their randomised treatment before week 24 should still be followed up through to week 24. For such patients, their week 24 data will be considered as primary, irrespective of treatment discontinuation, treatment interruption(s), use of rescue

medication (WLL or other), etc. The feasibility and likely meaningfulness of this analysis will be reviewed in the blind review of the SAP, once the extent and pattern of missing data are known.

A sensitivity analysis will include a mixed model for repeated measures including factors for treatment, visit, treatment-by-visit interaction, and baseline (A-a)DO₂.

Subjects who withdraw from the study early and who do not have week 24 data available will have their (A-a)DO₂ measurement imputed using multiple imputation for which full details will be given in the Statistical Analysis Plan. Further sensitivity analyses will include:

- “reasonably worst case” scenario. For the primary analysis, patients in either of the active arms will have the value of the 10th percentile from their dose arm imputed (i.e. approximately the 3rd worst case) whilst patients in the placebo arm will have the median for the placebo arm imputed.
- Tipping point analysis: Patients in any group with a missing endpoint will be assigned progressively worse (A-a)DO₂ to find the point at which the results reverse from favouring the active treatment to the placebo.

All attempts will be made to retain subjects in the trial, even if they wish to withdraw from trial treatment. Hence it is anticipated that there will be only minimal missing (A-a)DO₂ data at week 24 and a further sensitivity analysis will use all available Week 24 data with no imputation (i.e. a “completers” analysis).

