12.1.6 Key Secondary Efficacy Analyses

Absolute change from baseline in 6MWD and in SGRQ will be analysed using the same ANCOVA model as for (A-a)DO₂. Imputation for missing data will also follow the same rules as for (A-a)DO₂.

Time to WLL (time from randomisation to documentation that WLL needs to be carried out) will be analysed by the logrank test. The proportion of subjects in each group who require WLL at, or before, week 24 will be estimated, along with a 95% CI for the difference in rates between each active dose and placebo. Subjects who fulfil the criteria for rescue treatment but refuse (or for some other reason do not get) WLL, will be counted as if WLL was conducted. This decision will be documented when the trial is complete in the blind review of the SAP.

In addition, the hazard ratio and its 95% confidence interval will be estimated from a Cox model with covariates treatment, geographic region, and need for WLL within 2 months before randomisation.

Any patient who withdraws from the trial before week 24 and who has not needed a WLL will be considered as censored for the event of WLL. A sensitivity analysis will additionally be performed considering any such patients as having the endpoint event at the time they withdraw. All patients who reach week 24 and have not needed a WLL will be considered censored at week 24.

Further rules for handling missing data will be confirmed at the blind review of the SAP. Assuming that any subjects who withdraw from treatment remain in the trial, the Week 24 data will be considered as primary, regardless of adherence to treatment.

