5.3.6 Primary Efficacy analysis

The primary efficacy variable, (A-a)DO₂, will be collected at Screening, Baseline (randomisation), Week 4, 12 and 24 during treatment period, and at Week 12, 24, 36 and 48 during the follow-up period. All (A-a)DO₂ values reported in the CRF will be recalculated for statistical analyses using the equation:

$$Aa\ Gradient = \left(F_i O_2 (P_{atm} - P_{H_2O}) - \frac{P_a CO_2}{0.8} \right) - P_a O_2$$

where F_iO₂ is fraction of inspired oxygen

P_{atm} is ambient atmospheric pressure

P_{H₂O} is saturated vapour pressure of water at body temperature (set to 47 mmHg / 6.266 kPa)

P_aCO₂ is arterial partial pressure of carbon dioxide

P_aO₂ is arterial partial pressure of oxygen

Any of these assessments reported in kPa will be converted to a result in mmHg before the calculations, this will be done using a factor k=7.5.

The primary efficacy endpoint, absolute change from baseline of (A-a)DO₂ after 24-weeks treatment, will be analysed based on an ANCOVA model including treatment group, WLL (stratification), Japan vs other countries, and baseline (A-a)DO₂. The data from the three treatment groups will be analysed all together (all treatment groups included in one model). Contrasts will be set up to estimate treatment differences in change from baseline with 95% confidence intervals (CI) and the corresponding p-value for Molgramostim OD vs. Placebo and for Molgramostim intermittently vs. Placebo.

For each analysis two sided tests will be performed where the null hypothesis is that there is no difference between treatment groups, which will be tested against the alternative that

there is a difference. Control for type-1 error inflation due to multiple testing will be handled as described in section 5.4.

A de-facto estimand approach will be applied, where for the primary analysis, all observed data will be included, irrespective of subject adherence to the randomised treatment. Subjects who withdraw from their randomised treatment before week 24 will be followed up through to week 24, and their week 24 data will be considered as primary, irrespective of treatment discontinuation, treatment interruption(s), use of rescue medication (WLL or other), etc.

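### The SAP makes the observed-data ANCOVA the confirmatory test and multiple imputation supportive; the protocol points the other way, and SAP 5.1 does not declare the change

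*SAP*

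**What the plan says.** Both documents keep Week 24 values collected after treatment stop or rescue, so that is not at issue. They differ on subjects who have no Week 24 value.

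**Protocol.** The synopsis states: "Subjects who withdraw early will have (A-a)DO₂ measurement values imputed by multiple imputation used as their endpoint". Sensitivity analyses are mentioned only afterwards. Section 12.1.5 says that subjects who leave early without Week 24 data "will have their (A-a)DO₂ measurement imputed using multiple imputation for which full details will be given in the Statistical Analysis Plan", and later that "a further sensitivity analysis will use all available Week 24 data with no imputation". Section 12.1.6 carries this to 6MWD and SGRQ: "Imputation for missing data will also follow the same rules as for (A-a)DO₂". Section 12.1.3 mentions an observed-cases analysis only for the per-protocol set: "The efficacy variables will also be analysed using Observed Cases for the PPS".

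**SAP.** Section 5.3.6 sets the primary ANCOVA as one "where for the primary analysis, all observed data will be included, irrespective of subject adherence to the randomised treatment" and describes no imputation. MI is the second bullet under Sensitivity Analyses, which are declared supportive and outside the type I error procedure. Section 5.3.7 does the same for 6MWD and SGRQ. Section 5.6 describes the missing-data methods only as ways of judging the impact of missing data. In Appendix 1, Table 14.2.1.5 (ANCOVA) is the primary analysis and Table 14.2.1.7 (MI) is a sensitivity analysis.

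SAP 5.1 lists four changes from the protocol: the Japan covariate, extra subgroups, a sensitivity analysis for subjects who had WLL, and the number of WLLs as an endpoint. None concerns missing Week 24 data.

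**The concern.** The two analyses appear to have exchanged roles without a declaration. The once-daily versus placebo test of (A-a)DO₂ opens the hierarchy in SAP 5.4, so every later confirmatory claim depends on which p-value it uses.

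The full analysis set is all randomised subjects, but an observed-data Week 24 ANCOVA leaves out anyone without a Week 24 value and makes no use of that subject's Week 4 and Week 12 results. SAP 5.3.1 moves the assessments of early withdrawals to the visit nearest withdrawal. That is a sensible guard against carrying values forward, but it means that a subject who withdraws well before Week 24 has no Week 24 value. If dropout differs between arms in rate or mechanism, the observed-data comparison is biased, in a direction that cannot be known in advance.

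**Working it through.** **1. Text comparison**

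| | Protocol | SAP |
|---|---|---|
| Value for a subject with no Week 24 (A-a)DO₂ | MI value is the endpoint (synopsis; 12.1.5) | None in the main test (5.3.6) |
| No-imputation analysis of available Week 24 data | Sensitivity (12.1.5) | Main, confirmatory (5.3.6) |
| MI followed by ANCOVA | Main, as the synopsis reads | Supportive (5.3.6, Table 14.2.1.7) |
| 6MWD and SGRQ | Same imputation rules (12.1.6) | MI supportive (5.3.7) |
| Declared as a change | n/a | Not in 5.1 |

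Figure 2 of the SAP, which marks the main analyses, is not visible in the text reviewed, so this rests on the wording.

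**2. The plan's own figures**

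Power is taken from the noncentral t distribution. With n per group, df = 2n − 2 and noncentrality δ/(SD·√(2/n)).
- Primary endpoint (Protocol 12.2: δ 10, SD 7.5, α 0.01, 14 versus 28): power 90.8%. With 13 versus 26 it is 87.9%, so N = 42 reproduces.
- 6MWD (SAP Appendix 2: δ 50, SD 70.2, α 0.05): 43 per group gives 90.4% and 42 gives 89.7%, so 43 reproduces.
- SGRQ (δ 10, SD 10.1): 23 per group gives 90.7% and 22 gives 89.4%, so 23 reproduces.

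**3. Bias and type I error of the observed-data test**

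Assumptions, because the documents give no dropout figures: two arms of 45 (135/3), SD 7.5, correlation 0.7 between Weeks 12 and 24, and logistic dropout on the Week 12 change with slope 1 per SD. The ANCOVA includes treatment and baseline. MI uses 20 imputations by regression on baseline, treatment and Week 12. There were 6,000 null replicates per row. Simulation SE is 7.5·√(2/45)/√6000 = 0.02 mmHg for bias and √(0.05·0.95/6000) = 0.28 points for type I error.

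*(a) Same selective dropout in both arms, no treatment effect*

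| Missing | Observed-data bias (mmHg) | Type I error, observed data | Type I error, MI |
|---|---|---|---|
| 2% | 0.02 | 5.6% | 5.6% |
| 5% | 0.03 | 4.8% | 4.7% |
| 10% | −0.01 | 5.4% | 5.4% |
| 20% | 0.04 | 5.1% | 5.1% |

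There is no harm here.

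*(b) Selective loss on active, random loss on placebo, no treatment effect*

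| Missing | Bias towards drug (mmHg) | Two-sided type I error | False positives for drug (2.5% nominal) | MI bias (mmHg) | MI type I error |
|---|---|---|---|---|---|
| 2% | 0.11 | 4.8% | 2.8% | −0.01 | 4.5% |
| 5% | 0.24 | 5.3% | 3.5% | 0.01 | 5.0% |
| 10% | 0.45 | 6.2% | 4.9% | 0.02 | 4.9% |
| 20% | 0.88 | 7.9% | 7.1% | 0.02 | 5.1% |

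Repeat runs at 10% missing gave 0.40 to 0.49 mmHg. With correlation 0.5, 0.7 or 0.9 the 10% figure is 0.34, 0.49 or 0.59 mmHg.

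*(c) Unequal dropout rates, true effect 10 mmHg, 3,000 replicates*
- Placebo/active 10/5% and 20/5%: 0.25 and 0.64 mmHg against the drug.
- Placebo/active 5/10% and 5/20%: 0.22 and 0.72 mmHg towards it.
- MI stays within 0.06 mmHg, and power exceeds 99% with either method.

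**4. Power for 6MWD, the endpoint that set the new sample size**

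Observed data: n = 45·(1 − missing). MI, approximately: n = 45·(1 − missing·(1 − corr²)), with correlation 0.5 to 0.8.

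| Missing | Observed-data n | Observed-data power | MI power |
|---|---|---|---|
| 0% | 45 | 91.6% | 91.6% |
| 2% | 44.1 | 91.1% | 91.2–91.5% |
| 5% | 42.75 | 90.2% | 90.6–91.2% |
| 10% | 40.5 | 88.6% | 89.4–90.6% |
| 20% | 36 | 84.6% | 86.7–89.5% |

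The MI formula is slightly generous: a regression-estimator variance gives 86.4–89.2% in the last row. For SGRQ, observed-data power is 99.6% at n = 45 and 98.5% at n = 36.

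**The case against.** The strongest reply is that there was no change to declare. In Protocol 12.1.5 the MI sentence stands between the MMRM sensitivity analysis and a list of further sensitivity analyses, and the SAP keeps that order. Read alone, the section could make MI a sensitivity method. The ambiguity is real. But that reading leaves the synopsis statement without effect, and it leaves the protocol with no main method for these subjects, because the no-imputation analysis is itself labelled sensitivity. The observed-cases sentence in 12.1.3 is weaker support, since it concerns only the per-protocol set.

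Second, the protocol allows flexibility. Section 12.1 says of the blind review: "At that time, adjustments to the planned analyses may be identified based on, for example, the extent and timing of missing data". Section 12.3 lets a deviation be described and justified in an amendment, a revised SAP or the final report. This stands, so there is no breach yet. What is missing is the description and justification.

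Third, the harm may be slight. Section 12.1.5 says "it is anticipated that there will be only minimal missing (A-a)DO₂ data at week 24", and scenario (b) needs a dropout pattern that the documents do not predict. At 2% and 5% missing, its two-sided type I error is within simulation noise of 5%. MI also does well partly because dropout was made to depend on Week 12, which the imputation model contains; informative dropout beyond that was not tested. All of this limits the size of the concern.

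Fourth, the SAP already has a completer analysis. It also excludes subjects who discontinued treatment, so it is not the protocol's no-imputation analysis. Both can be reported.

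Finally, MI makes the gatekeeping p-value depend on a random seed. That is a fair cost, and the fix addresses it.

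**Conclusion.** The concern holds and should be fixed before unblinding. The SAP is internally consistent about its main analysis, but it is not the analysis the protocol points to, and SAP 5.1 is silent. MMRM, MI, tipping-point and worst-case analyses are all planned, so the gap is confined to which result carries the confirmatory p-value and which subjects are in it.

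The size depends on dropout figures that the documents do not give. Under the stated assumptions the observed-data test is unharmed by equal dropout. It is biased by about 0.1 to 0.9 mmHg at 2 to 20% missing when loss is selective on active only, and by 0.2 to 0.7 mmHg in either direction when rates differ between arms. Power for a 10 mmHg effect is not threatened. 6MWD power falls below its 90% target at 10% missing. If missing data are as few as the protocol expects, the practical effect is small.

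**What to change.** **Preferred.** In SAP 5.3.6 and 5.3.7, make MI followed by ANCOVA the main analysis for (A-a)DO₂, 6MWD and SGRQ. Keep the observed-data ANCOVA as the protocol's no-imputation sensitivity analysis, alongside the existing completer analysis. Exchange the labels of Tables 14.2.1.5 and 14.2.1.7, 14.2.2.4 and 14.2.2.6, and 14.2.2.22 and 14.2.2.24.

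Because MI would then carry a gatekeeping p-value:
- Add Japan versus other countries to the monotone regression step, which omits it although the ANCOVA includes it.
- Fix the seed and the order in which strata may be dropped.
- Pre-specify more than 10 imputations; the number is the sponsor's choice. In borderline simulated data sets (p 0.04 to 0.05, 10% missing), the seed alone moved p over about 0.032–0.065 with 10 imputations, 0.038–0.053 with 50 and 0.041–0.051 with 100. The share of seeds giving p > 0.05 was 32%, 14% and 9%.

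**Fallback.** If the observed-data ANCOVA stays primary, list and justify the change in SAP 5.1 and state that subjects with no Week 24 value are not in the test. This closes the documentation gap but leaves the exposure to unequal dropout.

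**Cost.** SAP wording, table labels and minor programming, with a slightly more complex primary analysis. The fallback is one entry in SAP 5.1. Neither option needs new data.

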All assessed (A-a)DO₂ measurements, and the corresponding changes from baseline will be summarised by visit and treatment group. In addition, similar summaries of (A-a)DO₂ will also be produced excluding data collected during treatment discontinuation, treatment interruption(s) and use of rescue medication (WLL or other). The decision of what data will be excluded and the reason will be identified during the blind review of data and documented in the "Pre-analysis-review"-document before data base lock (DBL).

Mean profiles for (A-a)DO₂ observed values and change from baseline over time will be provided.

Sensitivity Analyses

The following sensitivity analyses for the primary endpoint will be done in order to evaluate the robustness of the results in relation to influence of any missing data. The sensitivity analyses should be considered supportive analyses and will thus not be part of the procedures applied to control type-1 error rate for testing hypotheses for primary and key secondary efficacy endpoints as described in section 5.4.

- A mixed model for repeated measures (MMRM) will be applied including fixed, categorical effects for treatment, WLL (stratification), visit, treatment-by-visit interaction, Japan vs other countries, and fixed covariates for baseline (A-a)DO₂. An unstructured covariance matrix will be applied to model the within-subject errors, if possible. If this analysis fails to converge, compound symmetry will be tested. Kenward-Roger approximation will be used to estimate denominator degrees of freedom. This methodology does not require imputation of missing data. Instead missing data is modelled based on the subjects' available data and on other subjects' data over time (this approach is valid under assumption that data is missing according to 'Missing at Random' (MAR)) [2].

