5.5 Adjustment for Covariates

In all analyses of ‘change from baseline’, the corresponding baseline value of the parameter being analysed will be included in an analysis of covariance (ANCOVA) model. The WLL (stratification) will be included in all analysis models. For endpoints analysed by a mixed model for repeated measurements (MMRM), baseline will be included as a covariate in the model. Geographical region (as defined for subgroups), unique country or centre will not be adjusted for in the statistical analyses, instead adjustment will be made for Japan vs all other countries in all parametric analyses.

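### The MMRM sensitivity analysis holds baseline, WLL-stratum and Japan effects constant over visits, so its Week 24 contrast departs slightly from the primary ANCOVA even when no data are missing

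*SAP*

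**What the plan says.** **Primary model.** SAP 5.3.6 analyses the Week 24 change with an "ANCOVA model including treatment group, WLL (stratification), Japan vs other countries, and baseline" (A-a)DO₂. All covariate effects are therefore Week 24 effects.

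**MMRM.** The same section lists "fixed, categorical effects for treatment, WLL (stratification), visit, treatment-by-visit interaction, Japan vs other countries", with baseline (A-a)DO₂ as a fixed covariate. SAP 5.5 says only that "baseline will be included as a covariate in the model". Protocol 12.1.5 describes a "mixed model for repeated measures including factors for treatment, visit, treatment-by-visit interaction, and baseline" (A-a)DO₂. In all three places the only interaction with visit, where any is named, is treatment-by-visit.

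**Covariance and degrees of freedom.** "An unstructured covariance matrix will be applied to model the within-subject errors, if possible". Then: "If this analysis fails to converge, compound symmetry will be tested". No structure is named in between. "Kenward-Roger approximation will be used to estimate denominator degrees of freedom".

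**Purpose and status.** The sensitivity analyses are done "in order to evaluate the robustness of the results in relation to influence of any missing data". SAP 5.3.6 calls them supportive and places them outside the type I error procedure.

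**Companion analyses.** For (A-a)DO₂, multiple imputation (MI), the tipping point built on it and the reasonably-worst-case analysis all end in the primary ANCOVA. For 6MWD and SGRQ, SAP 5.3.7 keeps the MMRM, ANCOVA after MI, a completer analysis and a per-protocol analysis.

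**The concern.** A sensitivity analysis meant to show the influence of missing data is easiest to read if it returns the main result when nothing is missing. This MMRM does not, because it forces three covariate effects to be equal at Weeks 4, 12 and 24.

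The documents give some reason to doubt that equality:

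- Protocol 10.1.1 lets experienced sites use capillary samples at Weeks 4 and 12 but requires arterial samples at Baseline and Week 24.
- Protocol 5.2 reports a lag of 4–12 weeks before efficacy is seen and a maximum gas-exchange response at 24 weeks.
- The SGRQ symptoms component uses a 3-month recall (Protocol 10.1.7). At Week 4 most of that window lies before randomisation; at Week 24 none of it does.

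At stake is interpretation. A gap between MMRM and ANCOVA could be put down to missing data when part of it comes from the model. Protocol 12.1.5 expects little missing Week 24 data, which makes the model's share relatively larger.

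**Working it through.** The plan states no figure for this comparison, so there is nothing of its own to reproduce.

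**Inputs from the documents.** Post-baseline visits at Weeks 4, 12 and 24; 135 subjects, hence 45 per arm (SAP 3.1, 3.2); pre-treatment SD 7.4 mmHg (SAP 3.2).

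**Assumed, because the documents give none.** Slopes of change on baseline by visit, residual SDs by visit, AR(1) correlation 0.6–0.7, 15% in the WLL stratum, 25% in Japan.

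**1. Formula with baseline as the only covariate and complete data.** Let D be the raw Week 24 difference in mean change, Δ the difference in mean baseline, b₂₄ the fitted Week 24 slope and b* the MMRM's common slope.

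- ANCOVA contrast: D − b₂₄Δ
- MMRM contrast: D − b*Δ
- Gap (MMRM − ANCOVA): (b₂₄ − b*)Δ

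Here b* is the weighted mean of the visit slopes, with weights Σ⁻¹1/(1ᵀΣ⁻¹1), where Σ is the residual covariance. Randomisation gives Δ a mean of zero, so the gap is noise around zero, not bias. The RMS of Δ is 7.4 × √(2/45) = 1.56 mmHg.

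**2. Numbers.** The simulation used complete data, 45 per arm, all SAP covariates, unstructured covariance and 600 replicates per case. ANCOVA degrees of freedom stood in for Kenward-Roger.

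| Case | Slopes Wk 4/12/24 | SDs | Corr. | b* | b₂₄ − b* | Formula RMS = 1.56 × abs(b₂₄ − b*) | Simulated mean absolute gap (95th pct) | ANCOVA SE | SE ratio MMRM/ANCOVA |
|---|---|---|---|---|---|---|---|---|---|
| A | −0.3/−0.3/−0.3 | 7/7/7 | 0.6 | −0.30 | 0 | 0 | 0.10 (0.28) | 1.49 | 0.996 |
| B | −0.2/−0.4/−0.6 | 7/7/7 | 0.6 | −0.40 | −0.20 | 0.31 | 0.26 (0.65) | 1.49 | 1.018 |
| C | −0.2/−0.4/−0.6 | 5/7/9 | 0.6 | −0.25 | −0.35 | 0.55 | 0.46 (1.17) | 1.92 | 1.032 |
| D (stress) | −0.1/−0.4/−0.8 | 5/7/10 | 0.7 | −0.11 | −0.69 | 1.08 | 0.90 (2.33) | 2.12 | 1.114 |

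The weights are 0.42/0.17/0.42 in B, 0.85/0.04/0.11 in C and 0.98/0.02/0.00 in D. For a roughly normal gap the mean absolute value is about 0.80 × RMS. That gives 0.25, 0.44 and 0.87 for B, C and D, close to the simulation. The 0.10 in case A comes from sampling error in the slopes and from the other two constrained covariates.

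A second complete-data simulation, with equal and moderately changing slopes, gave an RMS gap of 0.13 (equal) and 0.29–0.58 (changing), against SEs of 1.5–1.9, with an SE loss of 0–5%. Case D lies outside that range: its slope changes eightfold and its SD doubles.

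**3. Bias and error rate.** Over A–D under unstructured covariance, the mean gap was at most 0.06 mmHg and type I error was 0.043–0.060.

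**4. Which terms close the gap.** Baseline-by-visit alone left a mean absolute gap of 0.07–0.16 mmHg (0.10–0.21 RMS in the second simulation). With all three covariates by visit the gap was 0.000 and the SE ratio 1.000. Theory agrees: 18 mean parameters are then 3 visits × 6, every visit has the same regressors with its own coefficients, and generalised least squares reduces to a separate regression at each visit. The Week 24 regression is the ANCOVA.

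**5. Against the effect of missing data.** Week 24 values were removed at random given earlier data (5% or 10%; 300 replicates). Entries are mean absolute gaps in mmHg.

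| Case | Missing | Due to missing data | Due to specification |
|---|---|---|---|
| A | 5% | 0.27 | 0.11 |
| A | 10% | 0.35 | 0.13 |
| C | 5% | 0.34 | 0.50 |
| C | 10% | 0.43 | 0.50 |

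**6. Fallback.** Under compound symmetry with the SAP's mean model, cases C and D gave Week 24 SEs of 0.81 and 0.79 of the ANCOVA SE, and type I error of 0.115 and 0.143. With equal SDs (A, B) the SE ratio was 1.00–1.02. For three visits, unstructured covariance has 6 parameters and compound symmetry 2.

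**The case against.** **A reader might infer that the plan cannot separate the effect of missing data.** The documents do not support that. The MI analyses re-use the primary ANCOVA for all three endpoints and, with nothing missing, return it exactly. For (A-a)DO₂ the tipping-point and reasonably-worst-case analyses do the same. The limitation belongs to the MMRM.

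**A reader might infer that the MMRM is biased or always less precise.** Neither follows. The gap averages zero, type I error under unstructured covariance is close to nominal, and there is no SE loss when slopes are equal.

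**A reader might infer that baseline-by-visit alone is the cure.** It is not, because WLL stratum and Japan are constrained in the same way.

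**The gap is small for decisions.** An RMS of 0.6 mmHg is 6% of the 10 mmHg planning difference. In a check with 135 subjects, equal SDs and correlation 0.65, MMRM and ANCOVA disagreed on significance in 0–0.4% of trials at a true effect of 10 mmHg. At 5 mmHg with steep slopes they disagreed in 7.6%. This stands: the issue matters mainly near the significance boundary.

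**The inputs are assumed.** This also stands. The SDs the SAP quotes before and after treatment, 7.4 and 7.6, are nearly equal. The capillary argument covers only some sites and only blood gases, so it says nothing about 6MWD or SGRQ.

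**The fallback may never be used.** Six covariance parameters with three visits and 135 subjects should normally converge. That makes the compound-symmetry point secondary.

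What remains is that the model differs from the main analysis for a reason unrelated to its stated purpose, and that the difference can be avoided.

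**Conclusion.** The point holds as an optional improvement. As written, the MMRM would differ from the primary ANCOVA at Week 24 with complete data, by about 0.1–0.6 mmHg RMS against an SE of about 1.5–1.9, with an SE loss of 0–5% that appears only when slopes change over visits. A deliberately steep case goes further. With slopes and SDs that change over visits, the specification gap can be as large as the gap caused by 5–10% missing Week 24 data; with equal slopes it is well below it.

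The size rests on assumed slopes, SDs and correlations. The direction of the argument does not: it follows from the model terms. The mmHg figures do not carry over to 6MWD or SGRQ, but the structural point does. No confirmatory test is affected.

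**What to change.** **Main change.** In SAP 5.3.6, add baseline-by-visit, WLL-stratum-by-visit and Japan-by-visit to the MMRM, apply the same model to 6MWD and SGRQ under 5.3.7, and align the sentence in 5.5. All three terms are needed for exact agreement with complete data. If the stratum or Japan terms cannot be estimated, keep baseline-by-visit as the minimum and say so in the output.

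**Secondary change.** If the unstructured matrix fails to converge, fit heterogeneous Toeplitz (5 parameters for three visits), then heterogeneous compound symmetry (4), and only then compound symmetry (2).

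**Cost.** One SAP sentence and one model line per endpoint. Each added interaction uses two parameters, six in all (from 12 to 18 mean parameters), with 135 planned subjects. No data collection, main analysis or testing order changes. The amendment should be made before unblinding and listed in SAP 5.1.
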